4.2 FINAL ANALYSES AND REPORTING

All final, planned analyses identified in the protocol and in this SAP will be performed only after the last subject has completed the End of Study visit or if the stopping criterion is met at the interim analysis. Key statistics and study results will be made available following database lock. Any post-hoc, exploratory (ancillary) analyses completed to support planned study analyses, which were not identified in this SAP, will be documented, and reported as necessary. Any results from these unplanned analyses will also be clearly identified as post-hoc analyses.

The Final Study Report is to be completed within 1 calendar month following the locking of the clinical database.

5 ANALYSIS POPULATIONS

5.1 HISTORICAL CONTROL POPULATION

The Historical Control Population (HC) for this study includes retrospective subjects that meet all inclusion and exclusion criteria except for the waist circumference and need for consent. Eligible subjects' electronic health records will be mined for the baseline, midpoint, and final study metrics.

The investigator or a designee will retrospectively review the site's electronic medical record (EMR) database to determine long-term care patient population's eligibility for meeting the study inclusion criteria. The subjects in the clinical site census at the time frame 6 months prior to the IRB approval date will be screened for eligibility for study inclusion.

If there is an insufficient number of eligible subjects to meet the control group target (defined as 2 times the expected number of intervention group subjects to be enrolled from the site) at 6 months prior to the intervention group start date, the EMR database screen will extend retrospectively in 6 month increments until the control group target is reached.

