- 2. Have experienced a fall-related fracture after age 50
 - Have experienced one or more falls in the 12-months prior to consent and have a diagnosis of osteoporosis, osteopenia, or prescribed osteoporosis medication.
- 3. Independently or with staff or caregiver assistance, able to transfer between surfaces (e.g., to or from a bed, chair, wheelchair, toilet, standing position) or walk or move between locations (use of an assistive device such as a walker is acceptable);
- 4. Have a waist circumference between 29 50 inches (63.5 127 cm);
- 5. Able to comply with required study procedures and follow-up schedule as determined by the Study Investigator;
- 6. Are under the care of the Investigational organization;
- 7. Provides consent or their legally authorized representative provides consent on subject's behalf

Exclusion Criteria (ANY of the following criteria):

- 1. Age 64 years or less;
- 2. Participation in a different clinical investigation that can conflict with this clinical study as determined by the Study Investigator and approved by the Sponsor;
- 3. Total dependence on staff or caregiver assistance to be able to transfer between surfaces (e.g. to or from a bed, chair, wheelchair, toilet, standing position) and walk and move between locations:
- 4. Use of other devices or interventions outside of SOC for fall risk management during study participation without Sponsor approval;
- 5. Unable to comply with required study procedures and follow-up schedule as determined by the Study Investigator;
- 6. Does not provide consent, or legally authorized representative does not provide consent

Investigational Device Tango® Belt

Route of Administration The Tango Belt is a device intended to be worn around the waist and is designed to:

- Recognize serious hip-impacting falls in progress
- Deploy an airbag upon detection of a serious hip-impacting fall in progress to protect the hip region from potential major injury
- Communicate fall and impact alerts to designated persons

Schedule of Visits The study is composed of the following study intervals:

Baseline Enrollment, screening, and provision of Tango Belt

14-day Run-in for adherence screening90-days EMR screening for endpoints

180-days EMR screening for endpoints and completion of participation

Table of Contents

Title Page 1					
List of Abbreviations and Definition of Terms 2					
Protocol Summary/Protocol Synopsis 3					
1.	Key Roles				
	1.1	Key roles listed	8		

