5.3 Strategies for Recruitment and Retention

Control group: The investigator or designee will retrospectively review the site's EMR database to determine their long-term care patient population's initial eligibility for meeting the study inclusion criteria. The subjects in the clinical site census at the time frame 6 months prior to the IRB approval date will be screened for eligibility for study inclusion. Subjects eligible for the control group must meet the requirements of the inclusion and exclusion criteria except for the waist circumference and need for consent. Eligible subjects' electronic health records will be mined for the baseline, midpoint, and

final study metrics. If there is an insufficient number of eligible subjects to meet the control group target (defined as 4 times the expected number of intervention group subjects to be enrolled from the site) at 6 months prior to the intervention group start date, the EMR database screen will extend retrospectively in 6 month increments until the control group target is reached.

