3.2 STUDY ENDPOINTS

3.2.1 PRIMARY ENDPOINT

The study's **primary effectiveness endpoint** is the proportion of major hip injuries due to fall in the subjects receiving SOC as compared to subjects receiving SOC plus the Tango Belt, as reported between enrollment and the 180-day visit.

There is no primary safety endpoint for this study. Safety of the device will be determined by analysis of adverse events as an ancillary endpoint.

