3.2.2 SECONDARY ENDPOINTS

The study's secondary endpoints include the proportion of each of the following:

- Hip fractures due to fall in the subjects receiving SOC as compared to subjects receiving SOC plus the Tango Belt.
- Emergency Department (ED) visits due to fall in the subjects receiving SOC as compared to subjects receiving SOC plus the Tango Belt.
- Hospitalizations due to fall in the subjects receiving SOC as compared to subjects receiving SOC plus the Tango Belt.

The secondary endpoints will be assessed using data reported between enrollment and the 180-day visit.

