7.1 Propensity Score Method

For each subject, a PS (i.e., predicted probability between 0 and 1) of intervention group membership (Tango Belt vs. SOC) will be calculated using a logistic regression, with "intervention group" as the outcome and the following baseline variables as the predictors: Age, mobility level, sex, and whether the subject fell in the past year.

Once propensity scores are calculated, propensity score matching (PSM) without replacement will be performed.

Subjects in the intervention group (i.e., Tango Belt) will be matched to controls with a similar PS using nearest neighbor matching (NNM) at a ratio of 1:2.

The PS modeling and design will be performed by a statistician who will be blinded to the endpoint data for each subject to avoid introducing bias into the analysis. The blinded endpoint data includes the primary and three secondary endpoints listed in section 3.2.

Balance of baseline variables (e.g., continuous variable, dichotomous variable, interaction terms, or squares of continuous variable) will be assessed by comparing the pre-matched and post-matched datasets.

Adequacy of propensity balance will be assessed by examination of standard differences between groups to confirm standard difference in post-matched dataset does not exceed 10%. Additionally, a comparison of the baseline covariate variables between groups after adjusting for propensity subgroup will be carried out as in D'Agostino et al. If the propensity matching is adequate, this will result in non-significant p-values (p>0.05) for the baseline characteristics.

Additional PS methods may be employed if group balance is not achieved by NNM, examples include covariate adjustment, inverse probability of treatment weighted (IPTW), etc.

Since enrollment may be ongoing at the time of interim analysis, propensity score modeling and matching will be conducted at the interim analysis and subjects will be rematched at the time of the final analysis to ensure the best PS match possible. With PS matching possibly occurring twice the following differences in PS modeling and design may occur:

- 1. Subjects may be matched to different control subjects.
- 2. The number of matches (1:1 or higher to a maximum of 1:4) may change based upon enrollment ratios.

3. The technique used to match (i.e., NNM) may change to another PS method to ensure adequacy of propensity balance.

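### Control eligibility has no index date, so a fall-related hip fracture inside the outcome window can both qualify a resident as a control and count as that control's endpoint

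*Combined protocol and SAP*

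**What the plan says.** Protocol 5.3 and SAP 5.1 exempt controls from two criteria only; SAP 5.1 describes them as "retrospective subjects that meet all inclusion and exclusion criteria except for the waist circumference and need for consent". Everything else in protocol 5.1 applies, including inclusion 2, which can be met in two ways:

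- Fracture route: "Have experienced a fall-related fracture after age 50". There is a lower limit (age 50) and no upper date.
- Fall route: "Have experienced one or more falls in the 12-months prior to consent", together with an osteoporosis or osteopenia diagnosis or osteoporosis medication. The look-back runs from consent.

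On timing, both documents say: "The subjects in the clinical site census at the time frame 6 months prior to the IRB approval date will be screened for eligibility". The same sections then judge whether there are enough eligible controls "at 6 months prior to the intervention group start date", which is a different anchor, and extend the search back in six-month steps if there are too few.

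The primary endpoint is counted "as reported between enrollment and the 180-day visit" (SAP 3.2.1). Enrollment is not defined for a control. The first secondary endpoint is "Hip fractures due to fall in the subjects receiving SOC as compared to subjects receiving SOC plus the Tango Belt" (SAP 3.2.2). The propensity model uses "Age, mobility level, sex, and whether the subject fell in the past year" (SAP 7.1).

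**The concern.** Belt subjects are screened, consented and put through a run-in before they are fully enrolled, so whatever meets inclusion 2 must come before their follow-up. For controls, the outcome window is already in the chart when eligibility is judged.

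Take a resident on the census list with no fracture history who falls and breaks a hip in month 3. On a literal reading at chart review, that resident has had a fall-related fracture after age 50 and is eligible. The same fracture is the first secondary endpoint. It is also a primary event if it leads to hospitalization, emergency care or medical intervention (the definition of major hip injury in protocol 2.2). The fall route has a similar gap: with no consent date, the reviewer must choose the date from which to look back, and nothing prevents the use of a fall, diagnosis or prescription recorded inside the window.

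The control rate is the comparator in SAP 7.2 and the sizing input in SAP 4 and 4.1.1. Selection that depends on the outcome cannot be repaired by matching: fracture history is not among the propensity covariates, and the event that admits the control is the event being compared.

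**Working it through.** **1. Does any text close the gap?**

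| Question | Belt subjects | Controls |
|---|---|---|
| When is inclusion 2 judged? | At screening, before full enrollment | At chart review, after the window |
| Upper date, fracture route | Implied by screening | None stated |
| Reference date, fall route | Consent | None (no consent is given) |
| Start of endpoint window | Enrollment | Not defined |

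The census date comes nearest. It selects the list of residents, but no sentence says that the criteria are read as of that date.

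**2. Reproducing the plan's figure, to see where the control rate enters.** Inputs from SAP 4 and 4.1: control proportion 15%, 80% reduction (3%), 1:2 allocation, 80% power, one-sided 0.025 with Pocock spending. Assuming the interim falls at half the information, the spend is 0.025 × ln(1 + (e − 1) × 0.5) = 0.0155, so z = 2.157.

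- Weighted mean proportion: (0.03 + 2 × 0.15)/3 = 0.11.
- n = [2.157 × √(1.5 × 0.11 × 0.89) + 0.842 × √(0.03 × 0.97 + 0.15 × 0.85/2)]² / 0.12² = 81.5.
- Continuity correction: (81.5/4) × [1 + √(1 + 6/(81.5 × 2 × 0.12))]² = 93.5, so 94 belt subjects and 188 controls, as stated.

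The same method for 60% protection (6% against 15%, nominal one-sided 0.0139) gives 185/370, close to the stated 188/376. Both sizes come directly from the control rate. They reproduce only if 15% is the six-month proportion; halved to 7.5%, the interim would need 198/396.

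**3. How large could the effect be?** The documents give no count of controls admitted through in-window records, so this is a range under assumptions.

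- p0 = 4%: six-month risk in properly eligible residents (8% a year, protocol 10.1, halved).
- M: otherwise ineligible residents on the census per eligible one (assumed).
- p′ = p0/2 = 2%: their risk (assumed). All their major hip injuries are taken to qualify them.
- q: number entering without a major hip injury, as a fraction of M, through a non-injurious fall with existing bone disease or through another fracture (assumed).
- The belt does nothing, so belt risk = p0.

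Control rate = (p0 + M p′)/(1 + M p′ + M q). With M = 1 this is 0.06/(1.02 + q). The rejection probability is the exact binomial probability for one unadjusted pooled z-test at one-sided 0.025, with 188 belt subjects and 376 controls. Without contamination it is 2.1%.

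| q (M = 1) | Control rate | Apparent reduction | Rejection |
|---|---|---|---|
| 0 | 0.06/1.02 = 5.9% | 32% | 14% |
| 0.1 | 0.06/1.12 = 5.4% | 25% | 9% |
| 0.2 | 0.06/1.22 = 4.9% | 19% | 6% |
| 0.4 | 0.06/1.42 = 4.2% | 5% | 3% |

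For other M, rejection at q = 0, 0.1, 0.2 and 0.4 is 6%, 5%, 4% and 2.5% with M = 0.5, and 39%, 21%, 11% and 3% with M = 2.

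The control rate returns to p0 when q = p′(1 − p0)/p0 = 0.5 × 0.96 = 0.48, whatever M is. Above that, the bias turns against the belt. The q = 0 row is therefore the upper bound for a given M.

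**4. Can the 15% rate be read as a trace of this?** Setting the q = 0 formula equal to 0.15 gives 0.017 M = 0.11, so M = 6.5. If 15% is annual (7.5% in six months), 0.0185 M = 0.035, so M = 1.9. The answer depends on how the rate is labelled and on a pool size that the documents do not give.

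**The case against.** Several passages point to reading the criteria at entry. Protocol 5.4 follows all subjects after enrollment to check that the criteria still hold, which presupposes that they held at the start. The wording in protocol 5.3 and SAP 5.1 about enough eligible residents six months before the start date can be read as dating eligibility itself. Controls have baseline metrics, and medical and fall history is a baseline item (protocol 7.2 and 7.3). An entry criterion is ordinarily read at entry. Screening data are independently reviewed (protocol 10.4) and eligibility is fully source-verified (protocol 11). The case report forms, which are not available here, may carry the dates.

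Much of this stands. The entry-date reading is the natural one, and a careful site would follow it. But none of these passages requires it, and source verification against the criterion as written would pass an in-window fracture. Blinding covers the propensity statistician and the injury adjudicator; the documents do not extend it to whoever screens the control charts.

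Four stronger readings should be resisted:

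- That the whole of inclusion 2 hangs on consent. Only the fall route does.
- That the propensity covariates are post-baseline. SAP 7.1 calls them baseline variables; what is missing is the calendar date of a control's baseline.
- That only injured residents gain entry. Non-injurious falls and other fractures would admit non-events too, and a hip injury without a fracture does not meet the fracture route.
- That the 15% rate, against the 6% to 10% a year expected, shows that this happened. The documents give no cause, and the annual versus six-month labelling is itself unsettled.

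**Conclusion.** The gap is real. As written, the rule allows a control to be admitted by the event that is then counted, and a belt subject cannot be. The likely direction favours the belt, but the size is unknown. Under the stated assumptions with M = 1 and a 4% risk, false rejection is at most about 14%, and 9%, 6% or 3% once 10%, 20% or 40% of the extra residents also enter without a major hip injury. A larger or smaller pool moves these figures up or down. They describe a single unadjusted look, not the planned matched logistic analysis with an interim. A reader might infer that enrolled controls were selected in this way or that the 15% is inflated; the documents support neither. What they support is that the rule must be closed, and the enrolled controls checked, before the control rate is relied on.

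**What to change.** In protocol 5.3 and SAP 5.1:

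- Give each control one index date, the census date actually used, and reconcile the two anchors (IRB approval and intervention start).
- For controls, replace the consent reference in inclusion 2 with the index date, and require the qualifying fracture, fall, diagnosis or prescription to be dated before it.
- Count control endpoints only from the index date to day 180.
- State in SAP 7.1 that the baseline propensity covariates, including a fall in the past year, are taken as of the index date.

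Then recheck the controls already enrolled against these dates, blind to outcome where possible. Remove those who qualify only through later records, and recompute the control rate before sample size re-estimation or any test.

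The cost is wording in two documents and a date check on charts that are already fully source-verified for eligibility. Some controls may be lost and the control rate may fall, which would raise the required sample size. If no control is affected, the recheck shows that and the rate stands.

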4.4 Endpoints

Primary Endpoint: The primary outcome measure will be the proportion of major hip injuries due to fall in the subjects receiving SOC as compared to subjects receiving SOC plus the Tango Belt.

Secondary Endpoints: Secondary outcome measures include the proportion of each of the following:

- Hip fractures due to fall in the subjects receiving SOC as compared to subjects receiving SOC plus the Tango Belt.
- Emergency Department visits due to fall in the subjects receiving SOC as compared to subjects receiving SOC plus the Tango Belt.
- Hospitalizations due to fall in the subjects receiving SOC as compared to subjects receiving SOC plus the Tango Belt.

Ancillary Endpoints: Ancillary endpoints will include:

- Adverse events
- Major injuries due to fall
- Fall occurrence
- Device wear adherence
- Device fall alerts
- Device discrimination of serious hip-impacting vs. non-serious hip and non-hip impacting falls
- Airbag deployment
- FES-I short version

5. Selection of Subjects

- **5.1 Inclusion Criteria**: All subjects are required to meet ALL of the following inclusion criteria to be considered eligible for participation in this study:
 - 1. Age 65 years or older;

- 2. Have experienced a fall-related fracture after age 50 -OR-
 - Have experienced one or more falls in the 12-months prior to consent and have a diagnosis of osteoporosis, osteopenia, or prescribed osteoporosis medication.
- Independently or with staff or caregiver assistance, able to transfer between surfaces (e.g., to or from a bed, chair, wheelchair, toilet, standing position) or walk or move between locations (use of an assistive device such as a walker is acceptable);
- 4. Have a waist circumference between 29 50 inches (63.5 127 cm);
- 5. Able to comply with required study procedures and follow-up schedule as determined by the Study Investigator;
- 6. Are under the care of the Investigational organization;
- 7. Provides consent or their legally authorized representative provides consent on subject's behalf
- **5.2 Exclusion Criteria**: Subjects will be excluded from participating in this study if they meet ANY of the following exclusion criteria:
 - 1. Age 64 years or less;
 - 2. Participation in a different clinical investigation that can conflict with this clinical study as determined by the Study Investigator and approved by the Sponsor;

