 - 3. Total dependence on staff or caregiver assistance to be able to transfer between surfaces (e.g., to or from a bed, chair, wheelchair, toilet, standing position) and walk and move between locations;
 - 4. Use of other devices or interventions outside of SOC for fall risk management during study participation without Sponsor approval;
 - 5. Unable to comply with required study procedures and follow-up schedule as determined by the Study Investigator;
 - 6. Does not provide consent, or legally authorized representative does not provide consent

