Intervention group: The investigator or designee will review the site's EMR database to determine their current long-term care patient population's initial eligibility for meeting all study inclusion and exclusion criteria, except for waist circumference, informed consent, and ability to comply. Subjects meeting initial eligibility will then have their waist circumference obtained, and those that meet inclusion criteria will then be offered the opportunity to participate in the study through the informed consent process utilizing IRB approved subject facing recruitment materials including a video introduction of the device, a flyer on the device and research study and verbal explanation of the study with access to study site investigator for addressing questions and/or concerns. If the subject agrees to be a participant in the study, the subject will be given a written informed consent to read, sign and date (Appendix 1 - Informed Consent). If the subject has a Legally Authorized Representative (LAR) or Person of Authority (POA) in place, the POA will receive notification regarding the eligibility for the subject to participate in the study with the IRB approved subject facing recruitment materials including video introduction of the device, a flyer on the device and research study and verbal explanation of the study with access to study site investigator for addressing questions and/or concerns with the written informed consent. The POA may offer consent verbally over the phone to the investigator/ designee with notation on the Informed Consent Form and subsequent receival of copy of the ICF via USPS or email. The ICF can also be signed electronically with a provided eSignature option to the POA. All subjects or POAs will be given the opportunity to discuss the technology, risks, potential benefits, alternative therapies, and the study requirements with the investigator prior to signing the informed consent. Subjects or their POAs that provide written or electronic consent will be preliminarily enrolled into the intervention group.

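### Historical controls must still pass the investigator's ability-to-comply judgement, undefined and unmasked for people known only from charts, so outcome-dependent selection of controls is not prevented

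*Combined protocol and SAP*

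**What the plan says.** **Controls.** Protocol 5.3 states that "Subjects eligible for the control group must meet the requirements of the inclusion and exclusion criteria" and then exempts two items, waist circumference and consent. SAP 5.1 repeats this: controls are "retrospective subjects that meet all inclusion and exclusion criteria except for the waist circumference and need for consent". Nothing else is waived. On who screens, SAP 5.1 says "The investigator or a designee will retrospectively review the site's electronic medical record (EMR) database". The same records then supply the baseline, midpoint and final metrics.

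**Criteria that therefore still apply to controls.**
- Inclusion 5 (protocol 5.1): "Able to comply with required study procedures and follow-up schedule as determined by the Study Investigator".
- Exclusion 5 (protocol 5.2): "Unable to comply with required study procedures and follow-up schedule as determined by the Study Investigator".
- Exclusion 4 (protocol 5.2): "Use of other devices or interventions outside of SOC for fall risk management during study participation without Sponsor approval".

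**Belt candidates.** Their record screen in protocol 5.3 covers "initial eligibility for meeting all study inclusion and exclusion criteria, except for waist circumference, informed consent, and ability to comply". The three deferred items are settled later, in contact with the candidate.

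**During follow-up.** Protocol 5.4 says that all subjects are followed for 6 months and that anyone who ceases to meet the criteria in that time is withdrawn. Controls are not excepted.

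**Masking and checks.** SAP 7.1 blinds the propensity score statistician to endpoints. Protocol 7.3 gives the injury adjudicator blinded data. Protocol 10.4 has an independent observer review screening data. Protocol section 11 requires source verification of enrolment criteria and the primary endpoint in every subject.

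**The concern.** Ability to comply is postponed for people who can be met and required for people who cannot. A control underwent no study procedures, so a site applying the criterion literally must decide, from a chart, whether a past resident would have complied. Neither document says which chart facts decide this, limits the review to entries before the index date, or keeps the screener from the outcome window.

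Exclusion 4 has a related problem. It refers to the period of study participation. For a control, the nearest equivalent is the six-month outcome window, so a device added after an injury could remove that control. The withdrawal rule in protocol 5.4 can be read the same way.

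In a non-randomised comparison the control rate drives both the treatment contrast and the sample size (SAP section 4). If membership of the control group depends on the outcome, even unintentionally, the control rate shifts and the test no longer has its nominal level or power.

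**Working it through.** The plan states no figure on this point. The check is a comparison of texts, followed by an illustration.

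**1. Items left out of the record screen**

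| Item | Belt candidates (protocol 5.3) | Controls (protocol 5.3, SAP 5.1) |
|---|---|---|
| Waist circumference | Deferred | Waived |
| Consent | Deferred | Waived |
| Ability to comply | Deferred | Neither waived nor deferred |

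**2. Timing.** The first control census is 6 months before IRB approval and follow-up is 180 days, so the window closes at about the approval date. Further censuses go back in 6-month steps. Screening done after approval therefore uses charts in which the window is complete or nearly so.

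**3. Do the stated safeguards reach this step?** The propensity statistician acts after controls are chosen. The adjudicator classifies injuries and does not select controls. The independent observer and source verification can confirm what was recorded, but neither is said to be masked to outcome or to precede selection.

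**4. Can matching repair it?** The propensity model in SAP 7.1 uses age, mobility level, sex and a fall in the past year. It contains no measure of compliance, and balance checks describe only those who were selected.

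**5. Illustration.** Inputs: a control proportion p = 0.15 (SAP section 4), a one-sided 0.025 test, and group sizes of 94/188 and 188/376 (SAP section 2). I take 15% as a six-month proportion because that reproduces the plan's 94: 3% v 15%, 1:2 allocation, 80% power, one-sided alpha 0.0155 (Pocock-type spending at half the information) and a continuity correction give 93.5, rounded up to 94. SAP 4.1 calls 15% an annual rate, so 7.5% is shown as well. The exclusion shares are assumptions; the documents give none.

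Let a be the share of uninjured and b the share of injured residents excluded. The observed control rate is

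p(1−b) / [p(1−b) + (1−p)(1−a)].

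- a = 0.20, b = 0.10: 0.135 / (0.135 + 0.680) = 16.6%. An inert belt at 15% would appear to give a reduction of 1 − 0.15/0.1656 = 9%.
- a = 0.10, b = 0.20: 0.120 / (0.120 + 0.765) = 13.6%.
- a = b: the rate stays at 15%.

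The chance of a significant result is Φ[(p_C − p_T − 1.96·SE0)/SE1], with SE0 pooled and SE1 unpooled. For a = 0.20, b = 0.10 at 188/376 with no true effect: (0.0156 − 1.96 × 0.0328)/0.0323 = −1.50, giving 0.066.

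| p | a (uninjured) | b (injured) | Control rate | Type I error, 94/188 | Type I error, 188/376 | Power for a 60% effect, 188/376 |
|---|---|---|---|---|---|---|
| 15% | 0 | 0 | 15.0% | 0.025 | 0.025 | 0.905 |
| 15% | 0.20 | 0.10 | 16.6% | 0.050 | 0.066 | 0.965 |
| 15% | 0.20 | 0 | 18.1% | 0.089 | 0.142 | 0.989 |
| 15% | 0.10 | 0.20 | 13.6% | 0.012 | 0.008 | 0.799 |
| 15% | 0 | 0.20 | 12.4% | 0.006 | 0.003 | 0.669 |
| 7.5% | 0 | 0 | 7.5% | 0.025 | 0.025 | 0.574 |
| 7.5% | 0.20 | 0.10 | 8.4% | 0.041 | 0.051 | 0.705 |
| 7.5% | 0.10 | 0.20 | 6.7% | 0.015 | 0.012 | 0.442 |

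These are single unadjusted tests at a nominal 0.025, without the interim look or matching.

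**The case against.** The best reply is that the compliance items may exclude no control at all. They concern study procedures and visits; controls have none, so the items could be read as trivially met. That reading is possible, and if every site took it there would be no selection through these items. The documents do not adopt it, though: they list what is waived for controls and leave compliance off the list.

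Second, protocol 5.3 and SAP 5.1 describe a census screened for eligibility, after which eligible subjects' records are mined. That order suggests eligibility comes first. It is not stated as a rule, however, and the same site staff use the same chart.

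Third, the observer review and full source verification are real safeguards. They would help to catch undocumented or inconsistent exclusions, but they do not mask the screener.

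Fourth, the exclusion shares are invented and the scenarios point both ways. That stands: they show what differential exclusion would do, not that it happened.

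The points on exclusion 4 and protocol 5.4 are weaker than the point on compliance. A control has no study participation in the ordinary sense, and the 5.4 rule is written for both groups. What stands is that neither text says how it applies to a control.

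**Conclusion.** The point holds as a gap in the plan. Controls are subject to an undefined, unmasked, retrospective compliance judgement, and two further rules can be read as acting on post-index events. Outcome-dependent selection is not prevented, and the matching cannot detect or correct it. Direction and size are unknown. Under the assumed splits of 20%/10% and 10%/20%, a 15% control rate moves to 16.6% or 13.6%; if exclusion is unrelated to outcome, nothing changes.

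Three stronger readings are not supported:
- A reader might infer that the protocol regards compliance as impossible to judge from a record. It only defers the item for belt candidates, which is natural when they can be seen in person.
- A reader might infer that investigators chose controls with the outcome in view. The documents leave the outcome visible but do not say that it was used.
- A reader might infer that the Sponsor-approval clause in exclusion 4 gave belt subjects extra protection. No approvals are described, and protocol 2.1 leaves unclear which other devices count as SOC, so no effect can be sized.

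The change should be made, but the point does not by itself show that the control rate is biased.

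**What to change.** 1. In protocol 5.3 and SAP 5.1, reconcile the control rule with the belt record screen. Either add inclusion 5 and exclusion 5 to the waived items, or define them for controls by a chart criterion dated before the index date.
2. Determine all control eligibility, including exclusion 4, only from records dated up to the index date, by a screener who has not seen the outcome window, and before outcomes are extracted.
3. State that the withdrawal rule in protocol 5.4 does not remove controls for post-index events.
4. SAP section 4 reports that roughly 70% of controls were already enrolled when the 15% rate was calculated, so wording alone is not enough. For controls already screened, log everyone excluded on these items, with the reason, and re-include them at least in a sensitivity analysis.

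The cost is wording in a few sections and some extra chart work. If the compliance items are waived, the control pool may include residents who would not have complied; the report should say so.
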